6.3.3.3 Sustained Pain Relief From 2 to 24 Hours Postdose

Sustained pain relief from 2 to 24 hours postdose is defined as pain intensity of none or mild at all time points from 2 to 24 hours postdose.

Subjects who meet all of the following criteria are classified as responders:

- Pain intensity of none or mild at all time points from 2 to 24 hours postdose, i.e., in the 2 to 24-hour postdose analysis windows
- Missing pain intensity at ≤ 1 time point from 3 to 8 hours postdose, i.e., in the 3, 4, 6, or 8-hour postdose analysis windows
- No rescue medication taken at or before 24 hours postdose, i.e., (1) rescue medication start date/time missing or (2) rescue medication start date/time $> \{\text{eDiary finding date/time for the pain intensity assessment in the 24-hour postdose analysis window}\}$.

Subjects who have any of the following are classified as failures:

- Rescue medication taken at or before 24 hours postdose (RM=F), i.e., (1) rescue medication start date/time $\leq \{\text{eDiary finding date/time for the pain intensity assessment in the 24-hour postdose analysis window}\}$, or (2) (rescue medication start date/time – study drug start date/time) ≤ 25 hours, the upper bound of the 24-hour postdose analysis window (see Section 7.3), if pain intensity is missing in the 24-hour postdose analysis window.
- Moderate or severe pain intensity at any time point from 2 to 24 hours postdose, i.e., in the 2, 3, 4, 6, 8 or 24-hour postdose analysis window
- Missing pain intensity at 2 or 24 hours postdose (NC=F), i.e., in the 2 or 24-hour postdose analysis window
- Missing pain intensity at > 1 time point from 3 to 8 hours postdose (NC1=F), i.e., in the 3, 4, 6, or 8-hour postdose analysis window.

Sustained pain relief from 2 to 24 hours outcomes are tabulated by treatment group as the number and percentage of subjects in the following categories:

- Responder: (1) Pain intensity of none or mild at all time points from 2 to 24 hours postdose, (2) missing pain intensity at ≤ 1 time point from 3 to 8 hours postdose, and (3) no rescue medication taken at or before 24 hours postdose
- Failure
 - Rescue medication taken at or before 24 hours postdose (RM=F)
 - Moderate or severe pain intensity at any time point from 2 to 24 hours postdose
 - Severe pain intensity
 - Moderate pain intensity
 - Missing pain intensity at 2 or 24 hours postdose (NC=F)
 - Missing pain intensity at > 1 time point from 3 to 8 hours postdose (NC1=F).

Failure subcategories are mutually exclusive, because subjects who meet more than 1 failure criterion are classified according to the first failure criterion met; in case of ties, the first failure subcategory that is met in the hierarchy above is chosen.

Treatment group comparisons of the percentage of subjects with sustained pain relief from 2 to 24 hours postdose use analogous methods as the main analysis of the co-primary endpoint of pain freedom with NC=F, NC1=F, and RM=F (see Section 6.3.2.1).

6.3.3.4 Sustained Pain Relief From 2 to 48 Hours Postdose

Sustained pain relief from 2 to 48 hours postdose is defined as pain intensity of none or mild at all time points from 2 to 48 hours postdose.

Subjects who meet all of the following criteria are classified as responders:

- Pain intensity of none or mild at all time points from 2 to 48 hours postdose, i.e., in the 2 to 48-hour postdose analysis windows
- Missing pain intensity at ≤ 1 time point from 3 to 8 hours postdose, i.e., in the 3, 4, 6, or 8-hour postdose analysis windows
- No rescue medication taken at or before 48 hours postdose, i.e., (1) rescue medication start date/time missing or (2) rescue medication start date/time $> \{\text{eDiary finding date/time for the pain intensity assessment in the 48-hour postdose analysis window}\}$.

Subjects who have any of the following are classified as failures:

- Rescue medication taken at or before 48 hours postdose (RM=F), i.e., (1) rescue medication start date/time $\leq \{\text{eDiary finding date/time for the pain intensity assessment in the 48-hour postdose analysis window}\}$, or (2) (rescue medication start date/time – study drug start date/time) ≤ 49 hours, the upper bound of the 48-hour postdose analysis window (see Section 7.3), if pain intensity is missing in the 48-hour postdose analysis window.

- Moderate or severe pain intensity at any time point from 2 to 48 hours postdose, i.e., in the 2, 3, 4, 6, 8, 24, or 48-hour postdose analysis window
- Missing pain intensity at 2, 24, or 48 hours postdose (NC=F), i.e., in the 2, 24, or 48-hour postdose analysis window
- Missing pain intensity at > 1 time point from 3 to 8 hours postdose (NC1=F), i.e., in the 3, 4, 6, or 8-hour postdose analysis window.

Sustained pain relief from 2 to 48 hours outcomes are tabulated for the efficacy analysis set by treatment group as the number and percentage of subjects in the following categories:

- Responder: (1) Pain intensity of none or mild at all time points from 2 to 48 hours postdose, (2) missing pain intensity at ≤ 1 time point from 3 to 8 hours postdose, and (3) no rescue medication taken at or before 48 hours postdose
- Failure
 - Rescue medication taken at or before 48 hours postdose (RM=F)
 - Moderate or severe pain intensity at any time point from 2 to 48 hours postdose
 - Severe pain intensity
 - Moderate pain intensity
 - Missing pain intensity at 2, 24, or 48 hours postdose (NC=F)
 - Missing pain intensity at > 1 time point from 3 to 8 hours postdose (NC1=F).

Failure subcategories are mutually exclusive, because subjects who meet more than 1 failure criterion are classified according to the first failure criterion met; in case of ties, the first failure subcategory in the hierarchy above is chosen.

Treatment group comparisons of the percentage of subjects with sustained pain relief from 2 to 48 hours postdose use analogous methods as the main analysis of the co-primary endpoint of pain freedom with NC=F, NC1=F, and RM=F (see Section 6.3.2.1).

6.3.3.5 Sustained Pain Freedom From 2 to 24 Hours Postdose

Sustained pain freedom from 2 to 24 hours postdose is defined as pain intensity of none at all time points from 2 to 24 hours postdose.

Subjects who meet all of the following criteria are classified as responders:

- Pain intensity of none at all time points from 2 to 24 hours postdose, i.e., in the 2 to 24-hour postdose analysis windows
- Missing pain intensity at ≤ 1 time point from 3 to 8 hours postdose, i.e., in the 3, 4, 6, or 8-hour postdose analysis windows
- No rescue medication taken at or before 24 hours postdose (see Section 6.3.3.3).

Subjects who have any of the following are classified as failures:

- Rescue medication taken at or before 24 hours postdose (RM=F; see Section 6.3.3.3)
- Mild, moderate, or severe pain intensity at any time point from 2 to 24 hours postdose, i.e., in the 2, 3, 4, 6, 8 or 24-hour postdose analysis window
- Missing pain intensity at 2 or 24 hours postdose (NC=F), i.e., in the 2 or 24-hour postdose analysis window
- Missing pain intensity at > 1 time point from 3 to 8 hours postdose (NC1=F), i.e., in the 3, 4, 6, or 8-hour postdose analysis window.

Sustained pain freedom from 2 to 24 hours outcomes are tabulated by treatment group as the number and percentage of subjects in the following categories:

- Responder: (1) Pain intensity of none at all time points from 2 to 24 hours postdose, (2) missing pain intensity at ≤ 1 time point from 3 to 8 hours postdose, and (3) no rescue medication taken at or before 24 hours postdose
- Failure
 - Rescue medication taken at or before 24 hours postdose (RM=F)
 - Mild, moderate or severe pain intensity at any time point from 2 to 24 hours postdose
 - Severe pain intensity
 - Moderate pain intensity
 - Mild pain intensity
 - Missing pain intensity at 2 or 24 hours postdose (NC=F)
 - Missing pain intensity at > 1 time point from 3 to 8 hours postdose (NC1=F).

Failure subcategories are mutually exclusive, because subjects who meet more than 1 failure criterion are classified according to the first failure criterion met; in case of ties, the first failure subcategory that is met in the hierarchy above is chosen.

Treatment group comparisons of the percentage of subjects with sustained pain freedom from 2 to 24 hours postdose use analogous methods as the main analysis of the co-primary endpoint of pain freedom with NC=F, NC1=F, and RM=F (see Section 6.3.2.1).

6.3.3.6 Sustained Pain Freedom From 2 to 48 Hours Postdose

Sustained pain freedom from 2 to 48 hours postdose is defined as pain intensity of none at all time points from 2 to 48 hours postdose.

Subjects who meet all of the following criteria are classified as responders:

- Pain intensity of none at all time points from 2 to 48 hours postdose, i.e., in the 2 to 48-hour postdose analysis windows

- Missing pain intensity at ≤ 1 time point from 3 to 8 hours postdose, i.e., in the 3, 4, 6, or 8-hour postdose analysis windows
- No rescue medication taken at or before 48 hours postdose (see Section 6.3.3.4).

Subjects who are not classified as responders and have any of the following are classified as failures:

- Rescue medication taken at or before 48 hours postdose (RM=F; see Section 6.3.3.4)
- Mild, moderate or severe pain at any time point from 2 to 48 hours postdose, i.e., in the 2, 3, 4, 6, 8, 24, or 48-hour postdose analysis window
- Missing pain intensity at 2, 24, or 48 hours postdose (NC=F), i.e., in the 2, 24, or 48-hour postdose analysis window
- Missing pain intensity at > 1 time point from 3 to 8 hours postdose (NC1=F), i.e., in the 3, 4, 6, or 8-hour postdose analysis window.

Sustained pain freedom from 2 to 48 hours outcomes are tabulated for the efficacy analysis set by treatment group as the number and percentage of subjects in the following categories:

- Responder: (1) Pain intensity of none at all time points from 2 to 48 hours postdose, (2) missing pain intensity at ≤ 1 time point from 3 to 8 hours postdose, and (3) no rescue medication taken at or before 48 hours postdose
- Failure
 - Rescue medication taken at or before 48 hours postdose (RM=F)
 - Mild, moderate, or severe pain intensity at any time point from 2 to 48 hours postdose
 - Severe pain intensity
 - Moderate pain intensity
 - Mild pain intensity
 - Missing pain intensity at 2, 24, or 48 hours postdose (NC=F)
 - Missing pain intensity at > 1 time point from 3 to 8 hours postdose (NC1=F).

Failure subcategories are mutually exclusive, because subjects who meet more than 1 failure criterion are classified according to the first failure criterion met; in case of ties, the first failure subcategory that is met in the hierarchy above is chosen.

Treatment group comparisons of the percentage of subjects with sustained pain freedom from 2 to 48 hours postdose use analogous methods as the main analysis of the co-primary endpoint of pain freedom with NC=F, NC1=F, and RM=F (see Section 6.3.2.1).

6.3.3.7 *Freedom from Photophobia, Phonophobia or Nausea at 2 Hours Postdose*

Freedom from each symptom (nausea, phonophobia, photophobia) at 2 hours postdose is assessed separately. Symptom status is measured as present or absent for each symptom (nausea, phonophobia, photophobia).

Symptom freedom at a single time point postdose is defined as a symptom absent at that time point for subjects with the symptom present at the time of dosing. Thus, all analyses of symptom freedom are based on the efficacy analysis set with the symptom present at the time of dosing (see Section 7.5.2), e.g., nausea freedom at a single time point postdose are based on subjects with nausea present at the time of dosing.

Symptom freedom outcomes at 2 hours postdose are tabulated by treatment group (see Section 6.3.4.1).

Treatment group comparisons of the percentage of subjects with symptom freedom at 2 hours postdose use analogous methods as the main analysis of the co-primary endpoint of pain freedom with NC=F and RM=F (see Section 6.3.2.1).

6.3.3.8 *Rescue Medication Use within 24 Hours Postdose*

Analyses are based on the evaluable efficacy analysis set, i.e., subjects in the efficacy analysis set with rescue medication start date on or before study drug start date + 1 day and missing rescue medication start time are excluded. Time to rescue medication use is measured from the study drug start date/time to the rescue medication start date/time.

No analysis window around the 24-hour postdose time point is used.

Rescue Medication Use within 24 Hours Postdose

Rescue medication use within 24 hours postdose is defined as time to rescue medication use ≤ 24 hours.

Treatment group comparisons of the percentage of subjects using rescue medication within 24 hours postdose use analogous methods as the main analysis of the co-primary endpoint of pain freedom, except that the NC=F and RM=F methods are not applied because they are not applicable to this endpoint (see Section 6.3.2.1).

Time to Rescue Medication Use through 24 Hours Postdose

Time to rescue medication use through 24 hours postdose is assessed by treatment group as follows:

- Kaplan-Meier plot and table using 2-hour time intervals (i.e., 0 to 2, > 2 to 4, ... , > 24). The Kaplan-Meier plot displays the percentage of subjects taking rescue medication within 24 hours postdose on the y-axis versus time in hours on the x-axis.

- Time-to-event distribution table (hours), including a log-rank p-value (zavegepant versus placebo).

See Section 6.1.1.1 for time-to-event plot and table attributes. Rescue medication use through 24-hours postdose is considered as an event in these time-to-event analyses. Subjects who do not take rescue medication within 24 hours postdose are censored at 24 hours and 1 minute (i.e., 1441 minutes).

6.3.3.9 *Pain Relapse from 2 to 48 Hours Postdose*

Pain relapse from 2 to 48 hours postdose is defined as pain intensity of mild, moderate, or severe at any time point postdose after 2 hours postdose for subjects with pain intensity of none at 2 hours postdose. Thus, analyses of pain relapse are based on the efficacy analysis set with pain freedom at 2 hours postdose (see Section 6.3.2.1).

Subjects who meet all of the following criteria are classified as non-relapsers:

- Pain intensity of none at all time points after 2 hours postdose, i.e., in the 3 to 48-hour postdose analysis windows
- Missing pain intensity at ≤ 1 time point after 2 hours postdose, i.e., in the 3, 4, 6, 8, 24, or 48-hour postdose analysis window
- No rescue medication taken at or before 48 hours postdose (see Section 6.3.3.4).

Subjects who have any of the following are classified as relapsers:

- Rescue medication taken at or before 48 hours postdose (RM=F; see Section 6.3.3.4)
- Mild, moderate, or severe pain intensity at any time point after 2 hours postdose, i.e., in the 3, 4, 6, 8, 24, or 48-hour postdose analysis window
- Missing pain intensity at > 1 time point after 2 hours postdose (NC1=F), i.e., in the 3, 4, 6, 8, 24, or 48-hour postdose analysis window.

Pain relapse from 2 to 48 hours outcomes are tabulated by treatment group as the number and percentage of subjects in the following categories:

- Non-relapser: (1) Pain intensity of none at all time points after 2 hours postdose, (2) missing pain intensity at ≤ 1 time point after 2 hours postdose, and (3) no rescue medication taken at or before 48 hours postdose
- Relapser
 - Rescue medication taken at or before 48 hours postdose (RM=F)
 - Mild, moderate, or severe pain intensity at any time point after 2 hours postdose
 - Severe pain intensity
 - Moderate pain intensity
 - Mild pain intensity

- Missing pain intensity at > 1 time point after 2 hours postdose (NC1=F).

Relapser subcategories are mutually exclusive, because subjects who meet more than 1 relapse criterion are classified according to the first relapse criterion met; in case of ties, the first relapse subcategory that is met in the hierarchy above is chosen.

Treatment group comparisons of the percentage of subjects with pain relapse from 2 to 48 hours postdose use analogous methods as the main analysis of the co-primary endpoint of pain freedom with NC1=F and RM=F (see Section 6.3.2.1).

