9.3.1 Efficacy Analyses

The intercurrent event of rescue medication use will be handled using RM=F, i.e., subjects who take rescue medication will be classified as failures for all efficacy assessments that are reported at or after taking rescue medication. The RM=F method will apply to all efficacy endpoints, except the secondary efficacy endpoint of rescue medication use within 24 hours postdose.

9.3.1.1 *Primary Endpoints*

Zavegepant will be tested for superiority against placebo at an $\alpha=0.05$ level for both co-primary endpoints using the efficacy analysis set. For each endpoint, treatment groups will be compared using a Cochran-Mantel Haenszel test to estimate the difference in percentages of subjects achieving the endpoint response criteria (zavegepant – placebo) stratified by prophylactic migraine medication use at randomization (yes or no). The percentage of subjects achieving the endpoint response criteria will be presented with a 95% confidence interval (CI) by treatment group. The difference in percentages between treatment groups will be presented with a 95% CI and p-value.

Subjects with missing data at 2 hours postdose will be classified as failures (i.e., Non-Completer = Failure; NC=F).

Sensitivity analyses will be described in the SAP.

9.3.1.2 *Secondary Endpoints*

If the tests of both co-primary endpoints are significant (i.e., both p-values are ≤ 0.05), then the secondary endpoints will be tested hierarchically at the $\alpha=0.05$ level in the order shown in the Secondary Endpoints section, using the efficacy analysis set. Thus, a secondary endpoint will be tested only if the preceding secondary endpoint in the hierarchy is determined to be significant (i.e., p-value ≤ 0.05). The same statistics will be presented as those for the co-primary endpoints.

For endpoints based on a single time point, such as phonophobia freedom at 2 hours postdose, subjects with missing data at a single time point will also be classified as failures. For endpoints based on multiple time points, such as sustained pain relief from 2 to 48 hours postdose, subjects with missing data at (1) 2, 24, or 48 hours postdose, or (2) more than 1 time point from 3 to 8 hours postdose will also be classified as failures.

9.3.2 *Safety Analyses*

Deaths will be listed without regard to onset for the enrolled analysis set.

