3.2.2 Secondary Objective Estimands

All secondary objectives have efficacy endpoints. The estimands corresponding to the secondary objectives are shown in [Table 2](#).

For each endpoint except rescue medication use within 24 hours postdose, intercurrent events are handled with a composite strategy described in Section 3.2. Subjects who take rescue medication are classified as failures for all efficacy assessments that are reported at or after taking rescue medication (see Section 6.3).

For each objective, the summary is the difference in the percentage of subjects achieving the endpoint response criteria between the zavegepant and placebo treatment groups using the efficacy analysis set.

Table 2: Secondary Objective Estimands

Objective Efficacy Endpoint	Pain relief at 15 minutes, 30 minutes, 60 minutes, and 2 hours postdose At each specified time point, percentage of subjects with a pain intensity of none or mild at time point
Objective Efficacy Endpoint	Return to normal function at 15 minutes, 30 minutes, 60 minutes, and 2 hours postdose At each specified time point, percentage of subjects with a functional disability level of normal at the time point; evaluated for subjects with functional disability at the time of dosing. Functional disability level is measured on a 4-point numeric rating scale (0=normal, 1=mildly impaired, 2=severely impaired, 3=requires bedrest), and functional disability are defined as mildly impaired, severely impaired, or requires bedrest.
Objective Efficacy Endpoint	Sustained pain relief from 2 to 24 hours postdose, and 2 to 48 hours postdose Percentage of subjects with pain intensities of none or mild at all time points from the start to the end of the time period of interest
Objective Efficacy Endpoint	Sustained pain freedom from 2 to 24 hours postdose, and from 2 to 48 hours postdose Percentage of subjects with pain intensities of none at all time points from the start to the end of the time period of interest
Objective Efficacy Endpoint	Phonophobia freedom at 2 hours postdose Percentage of subjects with phonophobia absent at 2 hours postdose; evaluated for subjects with phonophobia present at the time of dosing
Objective Efficacy Endpoint	Photophobia freedom at 2 hours postdose Percentage of subjects with photophobia absent at 2 hours postdose; evaluated for subjects with photophobia present at the time of dosing

Objective	Rescue medication use within 24 hours postdose

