5 SAMPLE SIZE, POWER, AND TYPE 1 ERROR

It is anticipated that about 90% of the 700 subjects randomized to each treatment group will have a headache in the allotted time period, resulting in approximately 630 subjects evaluable for efficacy in each treatment group.

The sample size calculation is based on results from the Phase 2/3 dose-ranging study BHV3500-201. The response rates for the pooled zavegepant 10 mg and 20 mg groups, and for the placebo group in study BHV3500-201 were 22.8% and 15.5%, respectively, for pain freedom at 2 hours postdose, and 42.2% and 33.7%, respectively, for MBS freedom at 2 hours postdose.

A total sample size of 1,260 evaluable subjects (630 per treatment group) provides approximately 91% power for the co-primary endpoint of pain freedom at 2 hours postdose, approximately 88% power for the co-primary endpoint of MBS freedom at 2 hours postdose, and approximately 80% power to detect a difference between treatment groups for both endpoints jointly.

Type I error is controlled by a hierarchical gate-keeping procedure. First, the family of 2 co-primary endpoints is tested. In particular, zavegepant is tested for superiority against placebo at an alpha=0.05 level for both co-primary endpoints. If the tests of both co-primary endpoints are significant (i.e., both p-values are ≤ 0.05), then the secondary endpoints are tested hierarchically at the alpha=0.05 level in the order shown in the Section 3.1.2, using the efficacy analysis set. Thus, a secondary endpoint is tested only if the preceding secondary endpoint in the hierarchy is determined to be significant (i.e., p-value ≤ 0.05). If a test in the hierarchy is not significant, then any further tests on endpoints in the sequence have p-values presented only for descriptive purposes, and no conclusions are drawn from those results.

For exploratory endpoints, no attempt is made to adjust for multiplicity. Any exploratory endpoints for which p-values are produced are evaluated at an unadjusted, 2-sided alpha=0.05 level and presented only for descriptive purposes.

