6.1.3 Missing Data

For all binary efficacy endpoints, main analyses impute missing data as failure using methods described in Section 6.3. Sensitivity analyses of the co-primary endpoints exclude subjects with missing data, or impute missing data using different methods (see Sections 6.3.2.1 and 6.3.2.2). Sensitivity analyses of exploratory efficacy endpoints exclude subjects with missing data (see Section 6.3.4.2). Otherwise, all analyses are based on observed data without using imputation.

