6.3.3 Secondary Efficacy Endpoints

All secondary efficacy endpoints are evaluated for the efficacy analysis set, unless specified otherwise.

If the co-primary endpoint tests are both significant for zavegepant versus placebo, then the secondary endpoints are tested for zavegepant versus placebo using a hierarchical gate-keeping procedure, with each test in the hierarchy conducted at $\alpha=0.05$. The endpoints are tested in the order shown in Section 3.1.2.

A by-subject listing of outcomes for pain relief, return to normal function, phonophobia freedom, photophobia freedom, and nausea freedom is provided for the randomized analysis set at each time point postdose. The listing also includes IWRS prophylactic migraine medication use at randomization and time to rescue medication start date/time in minutes (see Section 6.3.3.8), as well as functional disability level, phonophobia status, photophobia status, and nausea status at the time of dosing. See Section 6.3.4.1 for efficacy outcomes over time.

6.3.3.1 Pain Relief at 15 Minutes, 30 Minutes, 60 Minutes, and 2 Hours Postdose

Pain relief at a single time point postdose is defined as a pain intensity of none or mild at that time point.

Pain relief outcomes at 2 hours postdose are tabulated by treatment group (see Section 6.3.4.1).

At each time point postdose (15 minutes, 30 minutes, 60 minutes, and 2 hours), treatment group comparisons of the percentage of subjects with pain relief use analogous methods as the main analysis of the co-primary endpoint of pain freedom with NC=F and RM=F (see Section 6.3.2.1).

6.3.3.2 Return to Normal Function at 15 Minutes, 30 Minutes, 60 Minutes, and 2 Hours Postdose

Return to normal function at a single time point postdose is defined as a functional disability level of normal at that time point for subjects with functional disability at the time of dosing. Functional disability is defined as a functional disability level of mildly impaired, severely

impaired, or requires bedrest. Thus, all analyses of return to normal function are based on the efficacy analysis set with functional disability at the time of dosing (see Section 7.5.2).

Return to normal function outcomes at 2 hours postdose are tabulated by treatment group (see Section 6.3.4.1).

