7 CONVENTIONS

7.1 Derived Dates

Derived dates are defined as follows:

- Study drug start date/time: Earliest (1) study medication dose date and time from the eDiary Migraine Report, or (2) study medication intake date and time from the Study Medication Intake Report (see Section 7.5.1). This date is used to define analysis periods.
- Rescue medication start date/time: Earliest rescue medication date/time (see Section 6.2.6.2). Missing time is considered to be earlier than non-missing time on the same date.
- Imputed rescue medication start date/time: This is used only for time-to-event efficacy analyses in Section 6.3.4.3, and not for time to rescue medication use analyses in Section 6.3.3.8.
 - If the rescue medication start date and time are both not missing, then the imputed rescue medication start date/time is set to the rescue medication start date/time.
 - If the rescue medication start time is missing and the rescue medication start date is equal to the study drug start date, then the imputed rescue medication start date/time is set to the study drug start date/time.
 - Otherwise, if the rescue medication start time is missing and the rescue medication start date is equal to a postdose eDiary finding date with non-missing efficacy data, then the

imputed rescue medication start date/time is set to the first eDiary finding date/time corresponding to non-missing efficacy data.

- Otherwise, if the rescue medication start time is missing and rescue medication start date is equal to the study drug start date + 1 day, then the imputed rescue medication start date/time is set to the study drug start date/time + upper bound of the X -hour analysis window (see Table 5).
- COVID-19 visit date: (1) Complete visit date, if it exists; (2) otherwise, complete date the visit was planned to occur for a missed visit (see Section 9.1.1).
- Last contact date: (1) Earliest complete death date from AE CRFs, if it exists; (2) otherwise, the maximum complete date of the following: AE start or stop; COVID-19 visit only for in-person or remote visits; ECG; eDiary finding; eDiary study drug start; informed consent; IWRS randomization; laboratory collection; nasal inspection; non-study medication start or stop; physical measurement; procedure; rating scale; questionnaire; vital sign; visit. If the last contact date is after the most recent raw database creation date, then it is set to the most recent raw database creation date.

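### Secondary endpoint 15 (rescue use within 24 hours) drops subjects whose earliest rescue record is untimed, including some whose use is documented, so its analysis set is selected on the outcome

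*SAP*

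**What the plan says.** SAP 6.3.3.8 analyses endpoint 15 on a reduced set: subjects "with rescue medication start date on or before study drug start date + 1 day and missing rescue medication start time are excluded". An event is a time to rescue of 24 hours or less, and the Kaplan-Meier and log-rank analyses use the same set.

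SAP 7.1 derives one rescue start per subject: "Earliest rescue medication date/time (see Section 6.2.6.2). Missing time is considered to be earlier than non-missing time on the same date". It also defines an imputed rescue start, but "This is used only for time-to-event efficacy analyses in Section 6.3.4.3, and not for time to rescue medication use analyses in Section 6.3.3.8".

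Two other rules deal with untimed rescue. SAP 6.2.6.2 accepts an untimed record as rescue if it is dated on or after the dosing date. The RM=F rule in SAP 6.3 keeps subjects with untimed rescue and fails them by comparing dates.

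On the population, Protocol 9.3.1.2 tests the secondary endpoints "in the order shown in the Secondary Endpoints section, using the efficacy analysis set", and SAP 5 does so "in the order shown in the Section 3.1.2, using the efficacy analysis set". SAP 3.2.2 defines the summary as the difference "between the zavegepant and placebo treatment groups using the efficacy analysis set". SAP 6.3.3 leaves room for exceptions: "All secondary efficacy endpoints are evaluated for the efficacy analysis set, unless specified otherwise". On missing data, SAP 6.1.3 states: "For all binary efficacy endpoints, main analyses impute missing data as failure using methods described in Section 6.3".

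**The concern.** A subject with no rescue record can never meet the exclusion rule. Everyone removed has a rescue record dated on the dosing day or the next day, so membership of the analysis set depends on the outcome being measured. The excluded subjects fall into three groups:

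1. **Proven use.** A timed postdose record at 24 hours or less exists alongside the untimed one.
2. **Use under the SAP's own convention.** There is an untimed dosing-date record and no timed record at 24 hours or less. SAP 6.2.6.2 and RM=F treat this as rescue after study drug. If it was postdose, it was within 24 hours.
3. **Unknown.** The only possible evidence is an untimed next-day record. Protocol 5.5 permits rescue for a migraine that returns up to 48 hours, so use may fall on either side of 24 hours.

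Removing group 1, and group 2 under the SAP's convention, takes users out of both numerator and denominator and lowers the reported rescue rate. Removing group 3 can move the rate either way. The same untimed dosing-date record makes a subject a failure for sustained pain relief from 2 to 24 hours, yet removes that subject from the rescue endpoint. No sensitivity analysis covers the excluded subjects. Whether endpoints 16 and 17 are formally tested depends on endpoint 15.

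**Working it through.** **The plan's own figures.** The plan gives none for endpoint 15. Its power figures concern the co-primary endpoints and reproduce with 630 per arm: 0.910, 0.876 and a product of 0.796, against the stated 91%, 88% and 80%. Nothing below depends on them.

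**What the rule does.** Take a dose at 10:00 on day D, choose the earliest record under SAP 7.1, then apply SAP 6.3.3.8:

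| Rescue records | Derived start | Result |
|---|---|---|
| untimed D; timed D 14:00 (4 h) | untimed D | excluded, use proven |
| untimed D; timed D+1 08:00 (22 h) | untimed D | excluded, use proven |
| untimed D+1; timed D+1 08:00 (22 h) | untimed D+1 | excluded, use proven |
| untimed D only | untimed D | excluded |
| untimed D+1 only | untimed D+1 | excluded |
| timed D 14:00; untimed D+1 | timed D 14:00 | kept, counted as user |

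Any postdose time on day D is less than 24 hours after dosing. Day D+1 runs from 14 to 38 hours after a 10:00 dose, which is why group 3 is ambiguous.

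**Size.** All rates are assumptions. Let p be the share of an arm with a timed record at 24 hours or less or an untimed record dated D or D+1, m the share of those excluded, and g = 0.5 the share of the excluded in group 3, with n = 630 per arm (SAP 5).

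- Excluded: 630pm
- As written: p(1 − m)/(1 − pm), always below p
- Group 3 as users: p
- Group 3 as non-users: p(1 − gm)

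Example, p = 0.30 (zavegepant) and 0.40 (placebo), m = 0.20 in both: 0.24/0.94 = 25.5% and 0.32/0.92 = 34.8%, a difference of −9.25 points.

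Differences are zavegepant minus placebo, in points. The last column sets group 3 to users in one arm and non-users in the other.

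| p, % | m, % | Excluded | As written | Group 3 users | Group 3 non-users | Opposite settings |
|---|---|---|---|---|---|---|
| 30/40 | 5/5 | 9.5/12.6 | −9.84 | −10.0 | −9.75 | −9.0 to −10.75 |
| 30/40 | 10/10 | 18.9/25.2 | −9.66 | −10.0 | −9.5 | −8.0 to −11.5 |
| 30/40 | 20/20 | 37.8/50.4 | −9.25 | −10.0 | −9.0 | −6.0 to −13.0 |
| 30/40 | 10/20 | 18.9/50.4 | −6.95 | −10.0 | −7.5 | −6.0 to −11.5 |
| 30/40 | 20/10 | 37.8/25.2 | −11.97 | −10.0 | −11.0 | −8.0 to −13.0 |
| 70/80 | 20/20 | 88.2/100.8 | −11.07 | −10.0 | −9.0 | −2.0 to −17.0 |

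For the third row the opposite settings are 30 − 36 = −6 and 27 − 40 = −13. Giving both arms the same setting shows only −9 to −10.

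**Effect on the test** (unstratified pooled z-test). In all six rows the as-written p-value is 0.010 or less. Near the threshold it can change:

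- 34.5% vs 40%, m = 10% in both arms: 0.0509 as written, 0.0435 with group 3 as users, 0.0525 as non-users.
- 25% vs 32%, m = 5% and 15%: 0.073 as written, 0.006 with group 3 as users, 0.037 as non-users, and 0.067 with zavegepant group 3 as users and placebo group 3 as non-users.

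**The case against.** Much of the case on the other side stands.

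- **No contradiction between sections.** A reader might infer that SAP 6.3.3.8 conflicts with the stated analysis set and with SAP 6.1.3. It does not. SAP 6.3.3 allows a different set and 6.3.3.8 states one; 6.1.3 defers to the methods of Section 6.3, and 6.3.3.8 says that NC=F does not apply.
- **Group 2 is not proven use.** SAP 6.2.6.2 is a date convention, and some dosing-date records may be predose intake.
- **Same-direction sensitivity is not enough.** A reader might infer that setting group 3 to users and then to non-users in both arms bounds the effect. That bounds each arm's rate, not the treatment difference.
- **The SAP 7.1 imputed time is not a ready remedy.** For an untimed dosing-date record it equals the study drug start, so it would put events at minute 0 of the Kaplan-Meier curve. Protocol 5.5 prohibits other headache medication for the first 2 hours. SAP 7.1 bars this use.
- **Impact may be small.** Sites review the paper diaries before data entry (Protocol Table 1, footnote 5), so untimed records may be few. The documents give no reason to expect unequal shares in a double-blind trial. The excluded subjects remain in the rescue table and listing of SAP 6.2.6.2, although that table is descriptive and makes no 24-hour comparison.

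None of this justifies discarding group 1, whose outcome is documented, or treating the same group 2 record as rescue for other endpoints and as unusable here.

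**Conclusion.** The rule is flawed as stated: it selects the analysis set on the outcome and discards subjects whose use is proven or accepted elsewhere in the SAP. The severity is low. Endpoint 15 is tested only after both co-primaries and 14 other secondary endpoints succeed, and the co-primary analyses are untouched.

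The size rests wholly on assumed rates and on g = 0.5. With equal untimed shares at 30% vs 40%, the difference moves by at most 0.75 point from the result with group 3 as users, towards zero. With 10% and 20% untimed, in either order, it moves by 3.05 points (−6.95) or 1.97 points (−11.97). A change in the formal result needs rates near the threshold or unequal shares.

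A reader might infer that the rule favours zavegepant. The documents do not support that: it lowers both arms' rates relative to p, and the difference can shift either way.

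**What to change.** Revise SAP 6.3.3.8 for the binary endpoint:

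- Analyse the full efficacy analysis set.
- Count as a user anyone with a timed postdose rescue record at 24 hours or less, whatever untimed records exist.
- Count as a user anyone with an untimed dosing-date rescue record, as SAP 6.2.6.2 and RM=F do.
- Count group 3 as users in the main analysis, consistent with RM=F at a 24-hour assessment dated that day.
- Add sensitivity analyses with group 3 as non-users in both arms, and as users in one arm and non-users in the other, both ways round.
- Report the number in each group by arm.

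For the Kaplan-Meier and log-rank analyses, use the earliest timed record at 24 hours or less where one exists, and do not use the SAP 7.1 imputed time as an event time. Keep these analyses descriptive, on subjects with a known time or no use, and state by arm how many are left out.

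The cost is a few lines of SAP text, some programming and three sensitivity rows; no new data are needed. A few predose intakes may be counted as use, and the main analysis overstates use if some of group 3 took rescue after 24 hours. The sensitivity analyses show how much the group 3 assumption matters.
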